#### 9.4.2. Treatment Group Comparability

##### 9.4.2.1. Participant Disposition

A detailed description of participant disposition will be provided at the end of the study, including a summary of the number and percentage of patients entered into the study, enrolled in the study, and treated as well as number and percentage of patients completing the study, as

defined in the statistical analysis plan (SAP), or discontinuing (overall and by reason for discontinuation). A summary of all important protocol deviations will be provided.

#### **9.4.2.2. Participant Characteristics**

Demographic data are collected and reported to demonstrate that the study population represents the target patient population considered for regulatory approval. A summary of baseline patient and disease characteristics, historical diagnoses, preexisting conditions, and prior therapies will be reported using descriptive statistics.

#### **9.4.2.3. Concomitant Therapy**

A summary of prior and concomitant medications will be reported.

#### **9.4.2.4. Treatment Compliance**

Study treatment compliance will be assessed as the proportion of treatment that is actually taken, relative to what is expected, after accounting for protocol-defined dose adjustments. Study treatment taken will be derived from the difference between the total number of capsules/tablets dispensed and returned over the course of the patient's treatment. The number of cycles received, dose omissions, dose reductions, dose delays, and dose intensity will be summarized for all treated patients by treatment arm.

### **9.4.3. Efficacy Analyses**

#### **9.4.3.1. Primary Analyses**

Overall response rate is defined as the number of patients who achieve a best overall response of CR or PR divided by the total number of patients treated (safety population). The ORR, with 95% CI, will be summarized for each study part.

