Tumor markers	X		See Instructions											Collect tumor markers only for corresponding to cancer type: PSA- Prostate For mCRPC patients with nonmeasurable disease, PSA should be collected every 3 weeks (for the first 12 weeks of therapy) and evaluated every 9 weeks for progression after the first evaluation period (at 12 weeks). See Section 8.1.3 and Appendix 2 for further details.  CEA - Pancreatic CA-125 - Ovarian CA 19-9 - Pancreatic For other indications please collect relevant tumor markers (e.g., CA 19-9) Q6W

Baseline, On-Study and Post-Study Treatment Follow-up SoA														
	Baseline		Cycle = 21 days							Short-Term Follow Up a			Long-Term Follow-Up b	Instructions
	(Day Relative to C1D1)		Cycle 1				Cycle 2		Cycle 3-n	801	802	803	804-X	
			(±3 days)				(±3 days)		(±3 days)	30 day follow-up ±5 days	60 day follow-up ±5 days	90 day follow-up ±5 days	Q90D	
Procedure	≤28	≤7	D1	D2	D8	D15	D1	D2	D1					
														throughout the study (C1D1, C3D1, etc.). See Appendix 2.
Pregnancy test	X	≤24h	See Instructions							X	X	X		Applies only to women of childbearing potential. See Section 8.3.4. for pembrolizumab-specific requirements and Appendix 2. Pregnancy test required at monthly intervals during study treatment in both treatment arms and up to 120 days after study treatment discontinuation for patients receiving LY3475070 and pembrolizumab and at 7 days after study treatment discontinuation for patients receiving LY3475070 monotherapy per Section 8.3.4.
Tumor assessment-radiological imaging	X		See Instructions							See Instructions				Perform locally according to RECIST 1.1, using the same imaging method (e.g., CT or MRI) at each assessment every 9 weeks ± 7 days for the first year and every 12 weeks (±7 days) thereafter until a discontinuation criteria is met.
Radionuclide bone scan	X		See Instructions							See Instructions				Disease progression should be confirmed per iRECIST by the site 4 to 8 weeks after site-assessed first radiologic evidence of PD in clinically stable participants. Participants, who have unconfirmed disease progression may continue on treatment at the discretion of the investigator until progression is confirmed by the site. Note: Imaging must be performed within 28 days before C1D1. See Section 8.1

Baseline, On-Study and Post-Study Treatment Follow-up SoA														
	Baseline		Cycle = 21 days							Short-Term Follow Up a			Long-Term Follow-Up b	Instructions

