**Phase 1b:**

Objectives	Endpoints
Primary	

 
To establish the RP2D of LY3475070 as monotherapy and in combination treatment with pembrolizumab
 
To assess the safety, tolerability and clinical activity of LY3475070 as monotherapy and in combination with pembrolizumab
 
	
 
Assessment of safety including, but not limited to, TEAEs, SAEs, deaths, and clinical lab abnormalities per CTCAE v5.0
 
Investigator assessed ORR per RECIST v 1.1
 

Secondary	

 
To characterize the LY3475070 PK profile as monotherapy and in combination with pembrolizumab
 
	
 
<math>C_{max}</math>, trough (<math>C_{min}</math>, <math>C_{steady\ state}</math>), <math>AUC_{steady\ state}</math>
 

 
To characterize the clinical activity of LY3475070 as monotherapy and in combination with pembrolizumab as assessed by the investigator using RECIST v1.1
 
	
 
DOR
 
DCR
 
TTR
 
PFS
 
OS
 

Tertiary/Exploratory	

 
To assess the relationship between biomarkers, dose/exposure, and clinical outcomes
 
	
 
Results of biomarker assessments
 
Clinical outcomes data
 

 
To characterize the immune mediated anti-tumor activity of LY3475070 as monotherapy or in combination with pembrolizumab based on iRECIST criteria
 
	
 
iORR
 
iPFS
 
iDOR
 
iDCR
 

 
To evaluate the relationship between anti-tumor activity of LY3475070, as monotherapy and in combination with pembrolizumab, and biomarkers predicting efficacy and resistance in obtained tumor tissues or blood samples
 
	
 
Results of biomarker analyses
 
Clinical outcomes
 

 
To evaluate target occupancy of LY3475070
 
	
 
Percentage of target inhibition of adenosine in peripheral serum
 

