## Cohort E: Patients with mTNBC

- g) Prior PD-1/L1 inhibitor therapy allowed;
- h) Patients must have received treatment for metastatic disease (at least 1 regimen of cytotoxic chemotherapy for metastatic disease);

Participants are eligible to be included in the study only if **all** of the following criteria apply:

8. Must be able to provide informed consent, as described in Appendix 1, which includes compliance with the requirements and restrictions listed in the informed consent form (ICF) and in this protocol, according to local regulations and are at least 18 years of age.
9. Men with partners of childbearing potential must use a condom during intercourse. Men with partners of childbearing potential or women with childbearing potential must agree to use 2 effective methods of contraception including a highly effective contraceptive method of birth control (Appendix 3) during study treatment and for at least 120 days following the last dose of LY3475070 and pembrolizumab or country requirements, whichever is longer. For patients receiving LY3475070 only, contraception should be maintained for 7 days following the last dose. Additional guidance for contraception during and after study intervention are located in Appendix 3.
10. Women of childbearing potential must have a negative urine pregnancy test at the screening visit followed by a negative serum pregnancy test documented within 24 hours prior to initiation of treatment. If the screening urine test is positive or cannot be confirmed as negative, a serum pregnancy test will be required. Additional guidance for pregnancy testing during and after study intervention is located in Appendix 2 and Appendix 3.
11. Have at least 1 measurable lesion using standard techniques by RECIST version 1.1 (Eisenhauer et al. 2009). **Exception:** patients enrolled in the dose escalation phase and mCRPC patients enrolled in Cohort D1 and D2 are **not** required to have measurable disease.
12. Have a performance status (PS) of 0 or 1 on the Eastern Cooperative Oncology Group (ECOG) scale (Oken et al. 1982).
13. Previous treatments: Have discontinued all previous treatments for cancer and recovered from the acute effects of therapy (except alopecia). Patients must have discontinued from previous treatments, as shown below:

Previous Treatment	Length of Time Prior to First Dose of LY3475070
Endocrine therapies	$\geq 14$ days

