Best overall response (BOR; e.g., complete or partial response, stable disease or unknown) will be determined locally by the investigator per RECIST v1.1; there will be no independent review of BOR. When the RECIST v1.1 criteria for progressive disease are met, clinically stable patients may undergo additional radiologic imaging progression for confirmation of PD per iRECIST (Section 8.1.1, Seymour et al 2017). For patients who meet criteria to continue treatment after initial progression (either awaiting confirmation by iRECIST or have iUPD by iRECIST), reconsenting is required. Patients who discontinue treatment without documented progression should continue to be assessed for patients who discontinue study treatment without confirmed PD, periodic imaging per SoA (Section 1.3) for PD confirmation will continue until PD, or initiation of subsequent therapy or withdrawal of consent. If the patient is still on study treatment after 1 year, perform tumor imaging Q12W.

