### 8.1.3. Efficacy Assessment for mCRPC Patients

For mCRPC patients enrolled in this trial (both during dose escalation, Cohorts A and B, and dose expansion Cohorts D1 and D2), response criteria set forth by the Prostate Cancer Clinical Trials Working Group 3 will be utilized (Scher et al. 2016). Efficacy will be evaluated on a combination of RECIST v.1.1 (if patient has measurable disease), prostate-specific antigen (PSA) measurements, and bone scintigraphy using  $^{99m}\text{Tc}$ -methylene diphosphonate radionucleotide ( $^{99m}\text{Tc}$  MDP). Multi-parametric MRI may also be used to evaluate response or progression in bone-only disease. Central measurement of circulating tumor cells is planned at a frequency of every 3 weeks but will not be required for efficacy evaluation.

For patients with measurable disease, RECIST v1.1, as described above in Section 8.1.1, will be utilized with the following caveats:

- I. For nodal lesions, separate pelvic vs extra-pelvic disease and record up to 5 nodal lesions in total.
- II. In order to classify as progression, previously normal lymph nodes (<1 cm) must have grown by at least 0.5 cm in the short axis from baseline scan or nadir and be  $\geq 1$  cm in the short axis.
- III. Nodes that have progressed to  $\geq 1.5$  cm in the short axis are considered measurable; nodes that have progressed to 1 cm to <1.5 cm are considered pathologic but subject to clinical discretion and non-measurable.
- IV. Visceral disease should be designated separately as lung, liver, adrenal, or CNS.

All mCRPC patients will undergo a  $^{99m}\text{Tc}$  MDP scintigraphy at baseline to evaluate skeletal disease involvement. Bone lesions should be evaluated every 9 weeks ( $\pm 7$  days) and can be scheduled around CT/MRI disease staging. Due to possible bone flare that can be part of bone healing in response to treatment, and not actual progression, a 2+2 rule should be used for assessment. Progression should only be called if at least 2 new lesions are seen on the first on-treatment scan, followed by at least 2 additional lesions on the second or subsequent post-treatment scans.

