For patients with non-measurable disease, PSA evaluations will be utilized for response assessment to treatment. Prostate-specific antigen will be measured at each treatment cycle (every 3 weeks), but because favorable PSA response to treatment may be delayed, early PSA rises should be ignored until 12 weeks unless patient is rapidly progressing (new lesions on image assessment) with clinical deterioration. After the first evaluation at 12 weeks, PSA response should be evaluated at every 9 weeks for progression. A PSA increase of  $\geq 25\%$  and  $\geq 2$  ng/dL from baseline/nadir, confirmed with a second measurement at least 3 weeks apart, will be considered progression. A PSA decrease from baseline that is  $\geq 50\%$  will be considered a response and should be confirmed with a repeat measurement at least 3 weeks apart.

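### Cohort D's primary RECIST response rate counts mCRPC patients without measurable disease in its denominator, while their protocol-defined PSA response is never analysed

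*Protocol*

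**What the plan says.** **Who enters.** Protocol Section 5.1, criterion 11, requires a measurable lesion but makes an exception: "patients enrolled in the dose escalation phase and mCRPC patients enrolled in Cohort D1 and D2 are" not held to it. Admitting such mCRPC patients is the stated purpose of the current amendment.

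**How their response is assessed.** Section 8.1.3 says that the criteria of Prostate Cancer Clinical Trials Working Group 3 will be used for mCRPC. It then says: "Efficacy will be evaluated on a combination of RECIST v.1.1 (if patient has measurable disease), prostate-specific antigen (PSA) measurements" and bone scintigraphy. It adds: "Multi-parametric MRI may also be used to evaluate response or progression in bone-only disease". For the group in question: "For patients with non-measurable disease, PSA evaluations will be utilized for response assessment to treatment". A PSA fall from baseline of at least 50%, confirmed at least 3 weeks apart, is called a response.

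**What is analysed.** The Phase 1b primary efficacy endpoint (Section 3) is "Investigator assessed ORR per RECIST v 1.1", with no exception for Cohort D. Section 8.1.1 says of best overall response: "complete or partial response, stable disease or unknown) will be determined locally by the investigator per RECIST v1.1". Section 9.4.3.1 takes patients with a "best overall response of CR or PR divided by the total number of patients treated (safety population"), and SAP Section 6.7 does the same. Section 9 does not mention PSA.

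**The interim rule.** Section 9.5 plans an interim analysis of Cohort D with about 20 combination and 10 monotherapy patients. If no objective responses are seen in either arm, combination enrolment does not continue.

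**The concern.** Sections 8.1.3 and 9 do not fit together. Section 8.1.3 gives non-measurable patients their own measure of response. Section 9 leaves that measure out but keeps the same patients in the ORR denominator.

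Two things are at stake in Cohort D:

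- **The estimate.** Unless non-measurable patients reach CR or PR about as often as the others, the primary ORR depends partly on how many of them enrol. It could then not be compared cleanly between the arms, or with results in measurable disease.
- **The interim halt.** Expansion rests on the totality of the data, but the zero-response clause is worded as mandatory. If it counts RECIST responses, fewer patients can prevent the halt as the non-measurable share grows.

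Meanwhile a response that the protocol defines, and schedules PSA sampling for, would go unreported.

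**Working it through.** **1. The plan's own figures.** The table in Section 9.2 gives exact (Clopper-Pearson) 95% limits for N = 20 and N = 40. All ten rows reproduce to rounding. For example, 0/20 has upper limit 1 − 0.025^(1/20) = 0.168 (printed 0.17), and 5/20 gives 0.087 to 0.491 (printed 0.09 to 0.49).

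**2. Inputs.**
- From Section 9.5: about 20 + 10 = 30 patients at the Cohort D interim.
- Assumed, because the documents give no values: non-measurable share m = 0, 30, 50, 60%; RECIST ORR in measurable patients q = 10% or 20%, equal in both arms; CR rate in non-measurable patients c = 0 or 5%; complete response data.

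**3. Expected all-treated ORR** = q(1 − m) + c·m.

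| m | q = 10%, c = 0 | q = 20%, c = 0 | q = 10%, c = 5% |
|---|---|---|---|
| 0% | 10% | 20% | 10% |
| 30% | 7% | 14% | 7 + 1.5 = 8.5% |
| 50% | 5% | 10% | 5 + 2.5 = 7.5% |
| 60% | 4% | 8% | 4 + 3 = 7% |

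**4. Chance of no RECIST response among 30.** With k = 30(1 − m) measurable patients, P(0) = (1 − q)^k × (1 − c)^(30 − k).

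| m | k | q = 10%, c = 0 | q = 20%, c = 0 | q = 10%, c = 5% |
|---|---|---|---|---|
| 0% | 30 | 0.9^30 = 4.2% | 0.8^30 = 0.1% | 4.2% |
| 30% | 21 | 0.9^21 = 10.9% | 0.8^21 = 0.9% | 0.9^21 × 0.95^9 = 6.9% |
| 50% | 15 | 0.9^15 = 20.6% | 0.8^15 = 3.5% | 0.9^15 × 0.95^15 = 9.5% |
| 60% | 12 | 0.9^12 = 28.2% | 0.8^12 = 6.9% | 0.9^12 × 0.95^18 = 11.2% |

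The direction is the same in every column; the size depends heavily on q and c.

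**5. Effect of the denominator on one result.** Suppose 10 of 20 treated patients have measurable disease and 4 of those respond. The all-treated ORR is 4/20 = 20% (exact 95% CI 6 to 44%). The measurable-disease ORR is 4/10 = 40% (12 to 74%). The second is less precise but does not depend on enrolment mix.

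**The case against.** **An all-treated ORR is a usual, conservative choice.** That stands, and the denominator should be kept. What it lacks in Cohort D is a companion figure that does not move with enrolment mix.

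**Non-measurable patients may still reach a RECIST category.** A reader might infer that they cannot be responders, or that they must be recorded as unknown. The documents do not support that. Section 8.1.1 lists unknown only as an example and assigns nobody to it. The Schedule of Activities plans RECIST imaging with no exemption for non-measurable disease. Section 8.1.3 also relies on Working Group 3 criteria, a cited source that cannot be consulted here. Zero CR/PR is therefore an assumption, and the 5% column shows how much rests on it.

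**The halt rule is not badly ambiguous.** A reader might infer that a PSA fall could count under it. Section 9.5 speaks of objective responses, Section 9.1 of objective response rate, and Section 3 ties ORR to RECIST. Section 8.1.3 calls a PSA fall only a response. RECIST is the natural reading, so a sentence of clarification is enough. The clause also ends only further combination enrolment, and expansion is discretionary in any case.

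**No error rate is affected.** Section 9.1 rules out formal testing of ORR, so a reader should not infer any effect on alpha or power. With intervals this wide at N = 20, a shift from 10% to 7% is less than one patient (0.03 × 20 = 0.6).

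**The analysis could be added later.** Section 9.4.1 allows additional exploratory analyses and Section 9.4.6 further subgroup analyses, so a measurable-disease split is permitted. It is not prespecified.

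**Conclusion.** The point holds and should be fixed, though it does not invalidate the design. As written, Cohort D's primary ORR includes patients whom Section 8.1.3 assesses by another measure, and that measure appears in no planned analysis.

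If those patients contribute few or no CR/PR, the reported ORR is about q(1 − m). With half of the cohort non-measurable, a 10% rate is then reported as about 5%. Under the RECIST reading of the interim rule, the chance of a zero-response halt rises from 4.2% to 20.6% in that case. It rises only to 9.5% if non-measurable patients reach CR at 5%, and from 0.1% to 3.5% if measurable-disease ORR is 20%.

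The mismatch between sections can be read directly from the protocol. Its numerical size cannot: the shares and rates are assumed, so the figures are a range and not a prediction.

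**What to change.** For Cohort D, keep the all-treated ORR and add two prespecified analyses by arm:

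1. At the interim and final analyses, report beside it the RECIST ORR with exact 95% CI in treated patients with measurable disease at baseline. Measurability should be derivable from the baseline imaging that the protocol already requires.
2. Report separately the confirmed PSA response rate of Section 8.1.3, with exact 95% CI, in mCRPC patients with non-measurable disease. First reconcile the sampling text. The Schedule of Activities says "For mCRPC patients with nonmeasurable disease, PSA should be collected every 3 weeks (for the first 12 weeks of therapy"), with evaluation every 9 weeks afterwards, whereas Section 8.1.3 has PSA measured at each treatment cycle.

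**Cost.** Some wording, a little more analysis, and a wider interval for the measurable-disease ORR. For example, the upper limit is 0.31 for 0/10 (1 − 0.025^(1/10) = 0.308) against 0.17 for 0/20.

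Two clarifications are worth making in the same edit, though neither carries weight alone. Section 9.5 should state which responses count for Cohort D. The PFS censoring table in Section 9.4.3.2 rests on RECIST assessments; it should be reconciled with that section's own PFS definition, which admits clinical or radiological progression, and with the PSA and bone-scan progression rules of Section 8.1.3.

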#### **9.4.3.2. Secondary Analyses**

The **disease control rate** (DCR), defined as the proportion of patients who achieved a CR or PR or SD) out of all patients treated, will also be summarized. Best response is determined from a sequence of responses assessed. Two objective status determinations of CR before progression are required for a best response of CR. Two determinations of PR or better before progression, but not qualifying for a CR, are required for a best response of PR.

**Duration of response** (DoR) is defined as the time from the date measurement criteria for CR or PR (whichever is first recorded) are first met until the first date that disease is recurrent or objective progression is observed, per RECIST v1.1 criteria, or the date of death from any cause in the absence of objectively determined disease progression or recurrence. Duration of SD will be calculated only for patients with best response of SD. It is measured from the date of start of treatment to the date of first progression of disease or the date of death due to any cause, whichever is earlier. For each patient who is not known to have died or to have had a progression of disease as of the data-inclusion cut-off date, duration of SD will be censored at the date of last objective response assessment prior to the date of any subsequent systemic anticancer therapy.

**Progression-free survival** (PFS) is defined as the time from the date of start of treatment to the first date of the observed clinical or radiologically documented PD or death due to any cause,

whichever occurs first. For patients who are not known to have died or progressed as of the data-inclusion cut-off date, PFS time will be censored at the date of the last objective progression-free disease assessment prior to the date of any subsequent systematic anticancer therapy.

